**Table 1. Panitumumab Dose Reductions**

	Starting Dose	1 st Dose Reduction	2 nd Dose Reduction
Percentage (%)	100	80	60
mg/kg	6	4.8	3.6

#### 11.4.4 Criteria for Withholding a Dose of Panitumumab

##### Skin- or nail-related toxicities:

- Skin or nail infection requiring IV antibiotic or IV antifungal treatment
- Any skin- or nail-related serious adverse event

##### Non-skin- or nail-related toxicities:

Any grade 3 or 4 toxicity with the following exceptions:

- Panitumumab will only be withheld for symptomatic hypomagnesemia and/or hypocalcemia that persists despite aggressive magnesium and/or calcium replacement
- Panitumumab will only be withheld for grade 3 or 4 nausea, diarrhea, or vomiting that persists despite maximum supportive care
- Panitumumab will only be withheld for grade  $\geq 3$  anemia or grade 4 thrombocytopenia that cannot be managed by transfusion(s) or cytokine therapy

#### 11.4.5 Criteria for Re-treatment with Panitumumab

##### Skin- or nail-related toxicities:

Panitumumab administration may recommence once:

- The adverse event has improved to  $\leq$  Grade 2 or returned to baseline, or;
- The subject has recovered to the point where symptomatic skin- or nail-related toxicity is felt to be tolerable; or,

- Systemic steroids are no longer required, or
- IV antibiotic or IV antifungal treatment is no longer required

Non-skin- or nail-related toxicities:

Panitumumab administration may recommence once the adverse event has improved to  $\leq$  Grade 1 or returned to baseline.

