11.4.6 Dose Modification Schedule

- Subjects should be assessed for toxicity before each dose. Dose modification should be performed according to the schedule described below.
- Subjects who develop a toxicity that does not meet the criteria for withholding a dose of panitumumab (Section 11.4.4) should continue to receive panitumumab and their symptoms should be treated.
- Panitumumab-related toxicity will be considered resolved if it improves to a degree that allows for re-treatment with panitumumab (Section 11.4.5).

For subjects who experience a toxicity that meets the criteria for withholding a dose of panitumumab:

- Subjects receiving either 100% or 80% of the starting dose of panitumumab are allowed to have up to 2 subsequent doses withheld for toxicity. However a second dose should only be withheld if the toxicity has not resolved by the time that the subsequent dose is due.
- Subjects treated at the 100% dose level whose toxicity resolves after 1 dose of panitumumab is withheld should be re-started at the 100% dose level (recommended but not required, reduction to the 80% dose is allowed as an alternative to re-challenge with the 100% dose).
- If toxicity recurs, subjects treated at the 100% dose or 80% dose should be re-started at the 80% dose or 60% dose, respectively, when the toxicity resolves after withholding 1 or 2 doses of panitumumab.
- Subjects treated at the 100% dose level whose toxicity resolves only after 2 subsequent doses of panitumumab are withheld should be re-started at the 80% dose level.
- Subjects treated at the 80% dose level whose toxicity resolves after withholding 1 or 2 doses of panitumumab should be re-started at the 60% dose level.
- Subjects who experience toxicity at the 60% dose level will not be re-treated with panitumumab.

It is recommended that panitumumab doses will be escalated in subjects whose toxicity resolves to the degree that meets the criteria for re-starting a dose of panitumumab (Section 11.4.5). Dose escalations are recommended but not required. Dose escalations should occur in the following manner:

- Subjects treated at the 80% dose level whose toxicity does not recur should receive the 100% dose level at the next dose unless a previous attempt to re-escalate to the 100% dose level was not tolerated (re-initiation of the 80% dose is allowed as an alternative to dose escalation).

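### Sections 11.4.4 and 11.4.5–11.4.6 give conflicting answers on panitumumab for a patient whose skin or nail infection still needs IV treatment, and neither takes precedence

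*Combined protocol and SAP*

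**What the plan says.** **Hold.** Section 11.4.4 gives two skin or nail reasons to withhold a dose. One is "Skin or nail infection requiring IV antibiotic or IV antifungal treatment"; the other is any serious adverse event of the skin or nails.

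**Release.** The skin list in Section 11.4.5 begins "Panitumumab administration may recommence once: - The adverse event has improved to" Grade 2 or lower, or baseline. Three alternatives follow, each linked by 'or':
- "The subject has recovered to the point where symptomatic skin- or nail-related toxicity is felt to be tolerable; or"
- the end of any need for systemic steroids
- "IV antibiotic or IV antifungal treatment is no longer required"

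For toxicities other than skin or nail, the same section sets one test: Grade 1 or lower, or baseline.

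**What release means.** Section 11.4.6 states: "Panitumumab-related toxicity will be considered resolved if it improves to a degree that allows for re-treatment with panitumumab (Section 11.4.5". It adds that "a second dose should only be withheld if the toxicity has not resolved by the time that the subsequent dose is due". A patient at the 100% level who resolves after one withheld dose is to restart at 100%. That is a recommendation, and "reduction to the 80% dose is allowed as an alternative to re-challenge with the 100% dose". A patient at the 100% level "whose toxicity resolves only after 2 subsequent doses of panitumumab are withheld should be re-started at the 80% dose level".

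**Time limit.** Sections 11.4.6 and 11.4.7 rule out re-treatment more than six weeks after the previous dose. Section 11.4.7 also says that missed doses are not made up. Section 4.1 places panitumumab on Days 15 and 29 of a 5-week cycle.

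**The concern.** The condition that mirrors the infection trigger, the end of IV treatment, is only one of four alternatives. Read literally, the infection hold can lapse through a different condition while the infection is still being treated intravenously. Section 11.4.6 then carries that status forward, because its test for withholding the second dose is resolution under 11.4.5, not the trigger in 11.4.4.

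Tolerability describes symptoms; it does not show that an infection is controlled. Section 11.2 reports sepsis and septic death following severe skin toxicity, although it has no data on re-dosing during IV treatment. Patients also receive irinotecan and 5FU, for which Section 11.1 lists myelosuppression and neutropenia. The non-skin rule in 11.4.5 has no tolerability route, so the looser test applies to the hold that includes serious infection.

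**Working it through.** **1. The release rule for a patient still on IV treatment**

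Call the four conditions in 11.4.5: (a) Grade 2 or lower, or baseline; (b) recovered to tolerable; (c) systemic steroids no longer required; (d) IV treatment no longer required.

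As written, release = a or b or c or d. With IV treatment still required, d is false, so release = a or b or c.

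- (a) is open. It depends on the Appendix B grading, which is not shown.
- (b) can be met, but it needs a judgment that the patient has recovered to that point.
- (c) is met only if steroids were used and stopped, or if a condition that never applied is allowed to count.

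With d false there are 2 × 2 × 2 = 8 combinations of a, b and c, and 7 release the hold (all except none met). Leaving out (c) as doubtful, 3 of the 4 combinations of a and b release it. These are logical states, not patients or probabilities.

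The same patient on the same dose day:

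| Route | Answer |
|---|---|
| 11.4.4, re-applied at the pre-dose assessment | Withhold, because IV treatment is still required |
| 11.4.5 with 11.4.6, if (b) is judged met | Resolved; no ground to withhold the second dose |

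With the proposed rule, release = (a or b) and d where IV treatment caused the hold. With d false this is never met: 0 of 8.

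The dose at stake after one withheld dose at the 100% level is 6 mg/kg (recommended) or 0.80 × 6 = 4.8 mg/kg (allowed).

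**2. The six-week limit (separate point)**

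Inputs: doses on Days 15 and 29, 6 cycles (12 doses); cycle of 35 days (Sections 4.1, 9.1) or 36 days (Sections 1.0, 4.2); limit 6 × 7 = 42 days.

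With a 35-day cycle, doses fall on Days 15, 29, 50, 64, 85, 99, 120, 134, 155, 169, 190 and 204, so the gaps are 14 and 21 days.

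| | 35-day cycle | 36-day cycle |
|---|---|---|
| Gaps between doses | 14, 21 | 14, 22 |
| One missed | 14 + 21 = 35 | 14 + 22 = 36 |
| Two missed, first pattern | 14 + 21 + 14 = 49 | 14 + 22 + 14 = 50 |
| Two missed, second pattern | 21 + 14 + 21 = 56 | 22 + 14 + 22 = 58 |

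Nine consecutive pairs have a dose before and after. With a 35-day cycle, 5 give 49 days and 4 give 56. All 9 exceed 42, and so do all 9 with a 36-day cycle.

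For cycle length L with doses 14 days apart, two missed doses leave L + 14 or 2L − 14 days. Both are at most 42 only if L ≤ 28. The gloss in 11.4.7 equating two missed doses with four weeks fits dosing every 14 days (3 × 14 = 42), not this schedule.

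Time from the first withheld date to the limit is 42 − 21 = 21 or 42 − 14 = 28 days (42 − 22 = 20 or 28 with a 36-day cycle). If the second dose is delayed rather than skipped, 42 − 35 = 7 days remain after its due date (42 − 36 = 6).

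The alternative Day 1/Day 15 schedule in Section 11.4.2 has no stated cycle length. If it is 28 days (assumption), two missed doses leave 42 days, which is within the limit.

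**The case against.** The best defence is that the sections can be read together. Section 11.4.4 is framed per dose. Section 11.4.6 calls for toxicity assessment before each dose and tells staff to continue panitumumab only for toxicity that does not meet 11.4.4. Section 10.2 also requires adverse-event assessment before panitumumab. A patient still needing IV treatment meets 11.4.4 at that assessment. The release conditions may also have been meant to pair with different problems: tolerability echoes the dose-reduction wording in 11.4.3, and the end of IV treatment echoes the infection trigger. The release wording is permissive, and Section 13.6 lets the investigator stop treatment.

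Much of this stands. A reader might infer that the protocol instructs staff to dose during IV treatment, or that tolerability plainly ends the infection hold. The documents do not support either inference: 11.4.5 permits rather than requires, its tolerability condition includes recovery, and 11.4.4 can be re-applied on the day.

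The defence does not remove the conflict. The sentence that addresses the second dose tests resolution under 11.4.5. No text pairs conditions with reasons for hold, and the lists do not match: neither steroids nor tolerability is a trigger in 11.4.4. The safeguards, including dosing only under trial investigators (Section 5.6.1), make a wrong dose less likely but do not say which section governs.

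**Conclusion.** The concern holds as a conflict between sections, limited to the infection hold. Read literally, 11.4.5 with 11.4.6 can class a patient still on IV treatment as resolved, while 11.4.4 would withhold the dose, and neither is given precedence. This rests on the 'or' wording and on the 11.4.6 definition of resolution; it does not depend on the steroid condition or on Appendix B.

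The number affected cannot be derived. It is confined to those of the 39 Arm A patients whose infection still needs IV treatment when the next dose is due, probably few. For scale only: if the 12% monotherapy rate of severe skin toxicity in Section 11.2 carried over (assumption), 0.12 × 39 ≈ 5 patients would have any severe event, and this situation would be a subset of severe and infectious cases.

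A reader might extend the conflict to patients still on systemic steroids. Section 11.4.4 has no steroid trigger, so the documents do not support that.

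The interval point is separate and follows from the nominal schedule: on Days 15/29 the restart at 80% after two withheld doses contradicts the six-week limit. Neither point affects the sample size, the error rates or the 15-month RFS rule. The infection wording should be corrected because the potential harm is serious and the correction is cheap.

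**What to change.** **Section 11.4.5, skin and nail list.** Allow re-treatment only when the event is Grade 2 or lower, at baseline, or recovered to a tolerable level, AND, if IV antibiotic or antifungal treatment was the reason for the hold, that treatment is no longer required. State that a condition that never applied, such as steroids never used, cannot release a hold. Whether the end of systemic steroids should also be mandatory is the sponsor's clinical choice.

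**Cost.** This is a wording amendment with no added procedures or patients. A few Arm A patients would have a longer hold, and some may reach the six-week limit and lose panitumumab. That happens if re-dosing is not possible within 21 to 28 days of the first withheld date (20 to 28 with a 36-day cycle).

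**Sections 11.4.6 and 11.4.7, separately.** The simplest correction is to state that panitumumab stops after a second withheld dose on the Day 15/29 schedule, and to correct the four-week gloss. Setting a longer limit to suit the 5-week cycle would change a stopping rule. That is a clinical decision for the sponsor, and the infection wording need not wait for it.

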11.4.6 Dose Modification Schedule

- Subjects should be assessed for toxicity before each dose. Dose modification should be performed according to the schedule described below.
- Subjects who develop a toxicity that does not meet the criteria for withholding a dose of panitumumab (Section 11.4.4) should continue to receive panitumumab and their symptoms should be treated.
- Panitumumab-related toxicity will be considered resolved if it improves to a degree that allows for re-treatment with panitumumab (Section 11.4.5).

For subjects who experience a toxicity that meets the criteria for withholding a dose of panitumumab:

- Subjects receiving either 100% or 80% of the starting dose of panitumumab are allowed to have up to 2 subsequent doses withheld for toxicity. However a second dose should only be withheld if the toxicity has not resolved by the time that the subsequent dose is due.
- Subjects treated at the 100% dose level whose toxicity resolves after 1 dose of panitumumab is withheld should be re-started at the 100% dose level (recommended but not required, reduction to the 80% dose is allowed as an alternative to re-challenge with the 100% dose).
- If toxicity recurs, subjects treated at the 100% dose or 80% dose should be re-started at the 80% dose or 60% dose, respectively, when the toxicity resolves after withholding 1 or 2 doses of panitumumab.
- Subjects treated at the 100% dose level whose toxicity resolves only after 2 subsequent doses of panitumumab are withheld should be re-started at the 80% dose level.
- Subjects treated at the 80% dose level whose toxicity resolves after withholding 1 or 2 doses of panitumumab should be re-started at the 60% dose level.
- Subjects who experience toxicity at the 60% dose level will not be re-treated with panitumumab.

It is recommended that panitumumab doses will be escalated in subjects whose toxicity resolves to the degree that meets the criteria for re-starting a dose of panitumumab (Section 11.4.5). Dose escalations are recommended but not required. Dose escalations should occur in the following manner:

- Subjects treated at the 80% dose level whose toxicity does not recur should receive the 100% dose level at the next dose unless a previous attempt to re-escalate to the 100% dose level was not tolerated (re-initiation of the 80% dose is allowed as an alternative to dose escalation).
- Subjects treated at the 60% dose level whose toxicity does not recur should receive the 80% dose at the next dose unless a previous attempt to re-escalate to the 80% dose level was not tolerated (re-initiation of the 60% dose is allowed as an alternative to dose escalation).

- Subjects who miss more than 2 consecutive scheduled doses due to toxicity or are unable to receive a dose of panitumumab within 6 weeks of having received their previous dose of panitumumab due to toxicity will be considered unable to tolerate panitumumab and will not be retreated with panitumumab.
- If a subject demonstrates a clinical benefit with a documented response of stable disease, partial response or complete response and there are reasons that the dose modification rules above cannot be implemented, the investigator should contact and discuss these reasons with Amgen. The investigator must obtain written agreement from Amgen before any changes in the dose modification rules can be implemented.

#### 11.4.7 Panitumumab Delayed- or Missed-Doses

- Delays of panitumumab administration beyond 6 weeks from the previous dose of panitumumab are not allowed.
- Reasons to withhold a dose of panitumumab are described in Section 11.4.4. More than 2 consecutively missed doses (i.e. 4 weeks without panitumumab) are not allowed. Missed panitumumab doses will not be made up.

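### On the Day 15/29 schedule, every panitumumab restart after two withheld doses falls outside the 6-week limit in 11.4.7

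*Combined protocol and SAP*

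**What the plan says.** Section 4.1 places panitumumab on Days 15 and 29 and on no other day. Sections 4.1 and 9.1 give a 5-week cycle in which Day 36 is Day 1 of the next. Section 4.2 instead describes a cycle repeating every 36 days, for six cycles.

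Section 11.4.6 says that patients at the 100% or 80% dose level "are allowed to have up to 2 subsequent doses withheld for toxicity". Three restart instructions rely on that allowance:

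- Patients at 100% "whose toxicity resolves only after 2 subsequent doses of panitumumab are withheld should be re-started at the 80% dose level".
- Patients whose toxicity recurs step down one level "when the toxicity resolves after withholding 1 or 2 doses of panitumumab".
- Patients at 80% "whose toxicity resolves after withholding 1 or 2 doses of panitumumab should be re-started at the 60% dose level".

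The same section ends panitumumab permanently for patients who "miss more than 2 consecutive scheduled doses due to toxicity", or who, because of toxicity, cannot be dosed within 6 weeks of the previous dose.

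Section 11.4.7 adds three statements: "Delays of panitumumab administration beyond 6 weeks from the previous dose of panitumumab are not allowed"; "More than 2 consecutively missed doses (i.e. 4 weeks without panitumumab) are not allowed"; and "Missed panitumumab doses will not be made up". Its 6-week limit, unlike the one in 11.4.6, is not restricted to delays caused by toxicity.

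**The concern.** The count of withheld doses and the 6-week limit agree only if doses are evenly spaced 14 days apart. Here the gaps alternate between 14 and 21 days, so two withheld doses take longer than the limit allows. The restart instruction then falls due at a time when 11.4.7 permits no dose.

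The rule decides whether a patient on the panitumumab arm (39 planned) is re-exposed or stopped after toxicity serious enough to withhold the drug. With two instructions that cannot both be followed, one investigator could restart at 80% and another could stop for good, each citing the protocol.

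**Working it through.** **Inputs.** Dose days 15 and 29 (4.1). Cycle length 35 days (4.1, 9.1), with 36 days as a sensitivity case (4.2). Six cycles (4.1, 4.2). No make-up doses and a limit of 6 × 7 = 42 days from the previous dose (11.4.7). Up to two doses withheld (11.4.6).

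**The plan's own figure.** With dosing every 14 days, two missed doses give 2 × 14 = 28 days from the first missed dose to the restart, which is the stated 4 weeks. From last dose to restart is 3 × 14 = 42 days, exactly the 6-week limit. Both figures therefore reproduce on an every-2-week schedule.

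**The standard schedule.** Dose day = 35 × (cycle − 1) + 15 or 29, which gives 15, 29, 50, 64, 85, 99, 120, 134, 155, 169, 190, 204.

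| Doses withheld | Last dose to next scheduled dose | Holds within 42 days |
|---|---|---|
| 0 | 14 or 21 days | 11 of 11 |
| 1 | 35 days (15 to 50; 29 to 64) | 10 of 10 |
| 2 | 49 days (15 to 64) in 5 holds; 56 days (29 to 85) in 4 | 0 of 9 |

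The excess over 42 days is 7 or 14 days. With a literal 36-day cycle, one withheld dose gives 36 days. Two give 50 days (15 to 65) or 58 days (29 to 87), again 0 of 9 within the limit.

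**The 4-week remark.** Measured from first missed dose to restart, two missed doses span 35 days here (29 to 64; 50 to 85), against 28 days with every-2-week dosing.

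**Latest permitted restart.** A last dose on cycle 1 Day 15 gives 15 + 42 = study day 57, which is cycle 2 Day 22. A last dose on cycle 1 Day 29 gives 29 + 42 = study day 71, which is cycle 3 Day 1. Neither is a panitumumab day.

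**Treatment delays.** Every one-dose hold spans a cycle start, where 9.4 allows a delay of one to two weeks. The gap becomes 35 + 7 = 42 or 35 + 14 = 49 days (43 or 50 with the 36-day cycle). Section 11.4.6 counts only time lost to toxicity; 11.4.7 counts all of it.

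**The systemic-only schedule in 11.4.2.** If treatment on Days 1 and 15 means a 28-day cycle and panitumumab moves with it (neither is stated), a two-dose hold is 42 days, within the limit in 9 of 9 positions with no slack.

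**The case against.** The strongest reply is that 11.4.6 already answers the question. Its two stopping limits are joined by an or, so whichever is reached first applies, and the holds at issue are toxicity holds by definition. This stands where toxicity is still present at day 42: panitumumab stops and nothing is ambiguous. A reader might infer that every two-dose hold leaves the investigator without an answer; the text does not support that. It does not settle the case of a patient who has recovered by day 42 and is waiting only for the next scheduled day. That delay is arguably no longer due to toxicity, so 11.4.6 points to a restart while 11.4.7 still forbids the dose.

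A second reply is that the dose could be given early, or an exception agreed. Section 9.6 tolerates only minor, infrequent variations, and moving a dose forward by 7 or 14 days is hard to call minor. The exception in 11.4.6 needs a documented response or stable disease, and 12.1 says that response assessment is not appropriate after resection. Section 11.4.3 does allow doses to be delayed, but a delay lengthens the gap.

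Three other inferences go too far. One might say that a single missed dose already breaks the 4-week figure, because it leaves 35 days between doses. That compares a last-dose-to-next-dose interval with a first-missed-dose-to-restart interval; on the latter, one missed dose is 14 or 21 days. One might call the two-dose branches unusable throughout the trial; they may work on the systemic-only schedule. And one might read a threat to the efficacy result into this; nothing in the documents supports that.

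**Conclusion.** The inconsistency is real and should be corrected. On the standard schedule all 9 possible two-dose holds put the next scheduled dose 7 or 14 days past the 6-week limit (8 or 16 with a 36-day cycle). The 100%-to-80% branch, and the two-dose part of the other two branches, cannot be followed without breaching 11.4.7. The practical gap is the patient who recovers by day 42 with no dose due until day 49 or 56. The 4-week remark is also wrong for this schedule.

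This rests on dosing only on Days 15 and 29 with no make-up doses, as written. The documents give no rate of two-dose holds, so the number of patients affected cannot be estimated. No effect follows for the sample size, the 24-of-39 rule or the 15-month RFS analysis. The 6-week limit can be read as prevailing and as failing safe, since it prevents re-exposure, but no text ranks it above the restart instructions.

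**What to change.** - Add one sentence to 11.4.6 and 11.4.7: the 6-week limit from the previous panitumumab dose governs whatever the number of doses withheld, so on the Day 15/29 schedule only one dose (a 35-day gap) may be withheld before panitumumab is stopped.
- Limit the two-dose restart branches, and the wording on more than two missed doses, to patients on the systemic-only schedule in 11.4.2, provided that it is dosed every 14 days (a 42-day gap). Do not delete them outright, or those patients would have no restart rule. State there whether panitumumab follows that schedule.
- Remove the 4-week remark.
- State whether a treatment delay under 9.4 counts toward the 6 weeks. If it does, a one-dose hold plus a two-week delay (49 days) ends panitumumab.

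The cost is an amendment to the dosing rules, with no added patients, visits or procedures. The drug supplier may need to agree, since 11.4.6 requires its written agreement to changes in these rules. Patients whose toxicity resolves only around the second withheld dose lose a restart that 11.4.6 offers, though 11.4.7 already bars it.

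If the sponsor instead intends the two-dose restart to operate, the limit must rise to at least 8 weeks (56 days; 58 with a 36-day cycle). If a two-week delay is to fit as well, it must be 56 + 14 = 70 days (58 + 14 = 72). Either relaxes a safety limit and needs its own clinical justification.
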